- Impaired intellectual capacity (clinically determined)
- Serious chronic medical or psychiatric condition that, in the investigator's opinion, puts the subject at risk
- The subject has a significant skin condition at the procedure sites (i.e., hemangioma, scleroderma, psoriasis, rash, open wound or tattoo)
- The subject has an implant of any kind in the head (e.g. stent, clipped aneurysm, embolised AVM, implantable shunt – Hakim valve)
- Any use of light-activated drugs (photodynamic therapy) within 14 days prior to study enrollment
 - Visudine (verteporfin) – for age related macular degeneration
 - Aminolevulinic Acid- for actinic keratoses
 - Photofrin (porfimer sodium) – for esophageal cancer, non-small cell lung cancer
 - Levulan Kerastick (aminolevulinic acid HCl) – for actinic keratosis
 - 5-aminolevulinic acid (ALA)- for non-melanoma skin cancer
- The subject has any clinically unstable psychiatric conditions, is judged to be at serious suicidal risk, is determined by a clinician to have increased risk for suicidality due to medication washout, or if the clinician is concerned about washout of the light-activated drugs.
- Current treatment with a psychotropic medication on a dose that has not been stable for at least 4 weeks prior to initiating study treatment.
- Pregnant or nursing females
- Investigator and his/her immediate family

Study Population

Photobiomodulation for ASD in ADHD

The subject population for this study will consist of 90 subjects between the ages of 9 and 17 (inclusive), of any ethnic background, diagnosed with ADHD and presents with ATs of at least moderate severity. We will recruit subjects both internally and externally. Participants will be recruited from the pool of existing patients and new referrals to the Pediatric Psychopharmacology program and the Alan and Lorraine Bressler Clinical and Research Program for Autism Spectrum Disorders at MGH.

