Informed consent will be obtained prior to the performance of any protocol procedures and prior to subjects receiving the study treatment. The informed consent and assent documents will be used to explain in simple terms the risks and benefits of study participation to the subject and/or their parent/guardian. The nature of the study will be fully explained to the subject and/or their parent/guardian by a board-certified physician who is either the primary investigator or co-investigator. The subject and/or their parent/guardian will be encouraged to ask questions pertaining to their participation in the study and the subject and/or their parent/guardian may take as much time as they feel necessary to consider their participation in the study as well as consult with family members or their physician. Participation in this study is voluntary and the subjects and/or their parent/guardian may withdraw from the study at any time.

The IRB-approved informed consent documents will be signed and dated by the subject and the physician obtaining consent via Adobe eSignature. Subjects ages 14-17 will sign the same consent form as the parent, while subjects ages 9-13 will sign a separate assent form. If a subject turns 18 years old during the course of this study, he/she will be asked to sign the consent form again as an adult before continuing with the study. If the subject refuses to provide electronic consent after attaining majority status, he/she will be discontinued from the study.

The subject will meet all the inclusion criteria, have none of the exclusion criteria, and will provide their electronic signature on the Informed Consent and Assent documents (when applicable) to participate in this clinical study. Any subject that signs Informed Consent will be considered enrolled into the study, although they may not participate if they do not qualify for the study. In the event that a subject's or parent/guardian's ability to comprehend and communicate is compromised (per assessment of the Investigator), local regulations pertaining to Informed Consent signatures should be followed.

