This study is a 10-week, open-label, single treatment group designed to investigate efficacy, safety and tolerability of tPBM in treatment of ATs in youth with ADHD. The study may take up to 14 weeks from enrollment (allowing up to 4 weeks to schedule and complete initial screening and baseline visit).

Photobiomodulation for ASD in ADHD

If a potential subject's clinician ascertains that the patient has an interest in study participation, the clinician will offer contact information for the study to the patient and/or their parent/guardian. The patient and/or their parent/guardian can then contact the study coordinator for more information on the study. If the patient's physician is a member of study staff, the patient and his/her family will also be offered the opportunity to speak with another study physician who is not their treating clinician to review study details and consider participation. Clinical records are not scanned in order to recruit subjects.

After providing written informed consent, all subjects will complete a clinical diagnostic interview via a virtual visit with a board-certified study clinician to assess eligibility. A study clinician will complete the Reproductive Potential Form. All subject's parent/guardian will be administered an assessment battery including a brief demographic interview and the SRS-2.

If an additional family member of the subject is available, we will ask that family member to independently complete an SRS-2 form. Both forms will be scored and the form with the higher score will be used to determine subject eligibility in order to reduce the possibility of under-recognition of social impairment.

Study clinicians will complete a chart note at Weeks 0, 1, 2, 3, 4, 6, and 8. For a complete schedule of assessments, please refer to Table 1. The screening process may take place over multiple days, as necessary.

All data will be collected and entered into Research Electronic Data Capture (REDCap), an electronic data capture system that streamlines data collection and ensures data integrity. REDCap software allows researchers to design and implement study surveys electronically for collecting, storing, retrieving and manipulating data.

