Subject, parent/guardian and research staff will enter survey responses into the electronic assessment forms on REDCap. A member of study staff will send the forms for the parent/guardian to fill out via REDCap. The responses will be then transmitted securely via an encrypted connection and stored in a secured database. Electronic data capture eliminates the need for subsequent data entry by staff, thus minimizing human error. However, in the event that REDCap is unavailable or malfunctioning, study staff will print all study instruments and mail them to subjects and parent/guardian, thus study data will be collected in paper form.

Subjects will be instructed to administer daily tPBM treatments for 8 weeks. Each subject will be mailed a device to keep at home during study participation and return to study staff upon completion.

Concomitant Medications/Treatments

As part of the initial psychiatric evaluation, a detailed history of past and present treatments (pharmacological and non-pharmacological) will be obtained. At each study visit, subjects will be assessed for the use of concomitant medication. The guidelines for use of concomitant medications/treatments during the study are as follows:

- Participants may continue treatment with concomitant psychotropic medications (provided no exclusion criteria are met) and must remain on a stable dose during the course of the trial.
- Subjects requiring initiation of acute or chronic medication treatment may be discontinued from the study if treatment is judged by the investigator to interfere with the assessment of study drug effect.

- Non-pharmacological treatments such as supportive individual, family, or group therapy will be permitted provided they were in place for a substantial period of time (>1 month) prior to study enrollment and remain unchanged during the course of the trial.
- No new non-pharmacological treatments may be initiated during the course of the trial.

Washout Period

After the screening period, subjects who are currently taking any light-activated drugs, as noted in exclusion criteria, and willing to discontinue the use of their medication may do so in order to be eligible for participation in this study, if clinically appropriate per clinician judgment.

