Subjects will not be asked to discontinue their medication if it poses an increased risk for suicidality. If appropriate, medication washout will be recommended by our clinicians to participants and current providers. Medication washout will not occur without approval from the prescribing clinician. Clinician's will determine a washout schedule based on the half-life of the medication, the adverse effects associated with treatment and withdrawal, and an assessment of individual factors including duration on drug and dose. No subjects will be asked to discontinue ongoing exclusionary medications to participate in the study; however, if the subject is already tapering the medication off for clinical reasons at the time of screening and evaluation for participation, they will be considered eligible to participate only after the washout period as described. Our office does not take over care for the patient, but remains available during this time period. The washout schedule will be discussed with the participant and current providers.

Flexible Titration Schedule

Titration of tPBM will follow a flexible titration schedule with an option for slower titration, holding at lower dose, or lowering the dose based on tolerability and response to the tPBM as per clinician judgment. Dose will be adjusted upward per the flexible titration schedule provided the treatment is well tolerated. For the detailed titration schedule, please refer to Table II.

Subject Confidentiality

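### The light-activated-drug exclusion looks back from consent rather than from first irradiation, so it can miss the 14 days just before exposure, and it does not fit the washout text

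*Combined protocol and SAP*

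**What the plan says.** **The criterion.** Section III, Exclusion Criteria, rules out "Any use of light-activated drugs (photodynamic therapy) within 14 days prior to study enrollment" and lists examples of such drugs.

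**Its reference date.** Section IV, Subject Enrollment, states: "Any subject that signs Informed Consent will be considered enrolled into the study". It adds that such a person may still not take part if found not to qualify.

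**The time from there to exposure.** Section V, Study Design, gives a total of up to 14 weeks from enrolment, "allowing up to 4 weeks to schedule and complete initial screening and baseline visit". Tables I and II place the first irradiation at baseline (day 1).

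**When eligibility is checked.** Table I marks Inclusion/Exclusion Criteria at Screening only. It marks Concomitant Medications at every visit, Baseline included.

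**A neighbouring criterion.** The psychotropic-drug item in the same list has a different reference date: "Current treatment with a psychotropic medication on a dose that has not been stable for at least 4 weeks prior to initiating study treatment".

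**Washout.** The Washout Period section says that, after screening, subjects on a light-activated drug who are "willing to discontinue the use of their medication may do so in order to be eligible for participation in this study", if clinically appropriate. It goes on to say that clinicians will recommend washout where appropriate, and then: "No subjects will be asked to discontinue ongoing exclusionary medications to participate in the study". Subjects already tapering for clinical reasons become eligible only once the washout is over. Its length is left to the clinician.

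**The concern.** The evident purpose of the criterion is to keep light-activated drugs apart from irradiation of the forehead in minors treated at home. For that purpose the days that matter are those just before the first exposure. The window ends at consent, so it does not look at any day between consent and first irradiation. A listed drug used in that interval, even on the day before treatment, would not breach the criterion as written.

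The washout text raises a second problem. If a look-back is fixed at consent, stopping the drug later cannot alter whether it was met, yet the Washout Period section treats stopping after screening as a route to eligibility. Two study clinicians could apply these sections to the same child and reach opposite decisions.

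What is at stake is a safety rule and consistent eligibility decisions, not the efficacy estimate.

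**Working it through.** **Inputs**
- Look-back: 14 days, ending at enrolment (Exclusion Criteria).
- Enrolment: signature of consent (Subject Enrollment).
- Study length: "This study is a 10-week, open-label, single treatment group", that is 8 weeks of treatment plus 2 weeks to follow-up.
- Longest total from enrolment: 14 weeks (Study Design).
- First irradiation: day 1, at baseline (Tables I and II).

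**Step 1: reproduce the plan's timeline.** 8 + 2 = 10 weeks, and 10 + 4 = 14 weeks, as stated. The longest interval from consent to first irradiation is therefore 14 − 10 = 4 weeks = 28 days.

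**Step 2: what the criterion covers.** Let g be the number of days from consent to first irradiation.
- Of the 14 days just before irradiation, the number not covered is min(g, 14).
- Use that ended before consent passes only if it ended at least 14 days before consent, so it ended at least 14 + g days before irradiation.

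| g (days) | Uncovered days among the 14 before irradiation | Shortest interval to irradiation for permitted use that ended before consent (days) |
|---|---|---|
| 0 | 0 | 14 |
| 7 | 7 | 21 |
| 14 | 14 | 28 |
| 21 | 14 | 35 |
| 28 | 14 | 42 |

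For past use, the consent date is never the looser choice. The gap concerns only use on or after the day of consent, and against a 14-day window before exposure it is at most 14 days. For comparison, the same 14 days counted back from first irradiation would leave 0 days uncovered at every g. That shows what drives the gap; it is not a proposal for the rule.

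**Step 3: the washout sections side by side.**
- *Criterion with enrolment definition:* a subject using the drug at consent has use inside the 14 days and fails. Nothing that happens later changes that look-back.
- *Washout Period, opening:* the same subject may stop after screening, hence after consent, and so become eligible.
- *Washout Period, continuation:* clinicians will recommend washout where appropriate, but no subject will be asked to discontinue.

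The first two do not fit together on the literal wording. The third is in tension with itself. A subject who enters by the washout route also has no stated minimum drug-free interval before irradiation, because the only number of days given is tied to consent.

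**The case against.** The strongest reply is that the interval is not unsupervised.
- The Exclusion Criteria also remove anyone whose washout of a light-activated drug worries the clinician.
- Medications are reviewed at every visit, including Baseline.
- A subject who starts a new medication may be discontinued.
- Subjects already tapering must finish washout first.
- Subjects found ineligible may be withdrawn.

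This stands in part: the safeguards exist and make an unnoticed case less likely. But they are discretionary or cover only some subjects, and none is tied to this criterion. The new-medication rule asks whether the drug interferes with assessing the study treatment's effect, not whether it is light-activated. The tapering rule does not reach a drug started after consent.

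A second reply is that the psychotropic comparison proves no error, since the two criteria serve different ends and the rule on non-drug therapies also counts from enrolment. That is fair. The comparison shows only that the list already uses a treatment-start reference date where exposure timing matters.

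A third reply is rarity. The listed indications are conditions such as age-related macular degeneration, actinic keratosis and cancers, while subjects are aged 9 to 17. This stands, and it limits the weight of the point.

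A reader might also draw two stronger conclusions that the documents do not support.
- *A user at consent is barred for good.* No section forbids screening or consenting again, and the Washout Period section plainly expects some users to become eligible.
- *Only subjects already tapering may enter after washout.* The word on which this rests governs when such subjects become eligible, not who may do so. A willing subject stopping and nobody being asked to stop can be read together as voluntary against requested. What remains unresolved is recommending against not asking.

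**Conclusion.** The point holds as a minor safety and eligibility correction. As written, the criterion does not catch use of a light-activated drug between consent and first irradiation. Between 0 and 14 of the 14 days before exposure are uncovered, depending on the gap, and all 14 once it reaches 2 weeks. The washout text conflicts with a look-back fixed at consent and is not consistent about whether subjects are encouraged to stop.

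A reader might take the 4-week allowance to mean a 28-day shortfall. That is the longest possible interval between consent and baseline, not the typical one, and measured against the criterion's own 14 days the shortfall cannot exceed 14. Nor does the point reach the results: it does not touch the sample size, the power or the SRS-2 analysis.

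Assumptions: enrolment in the criterion carries the meaning given in Subject Enrollment, and irradiation begins at baseline as Tables I and II show. That cases at these ages are few is a further assumption, since the documents give no frequency.

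**What to change.** 1. The clinical team should reconcile the Exclusion Criteria, the enrolment definition and the Washout Period section so that they give one reference date for the window and one statement of who may enter after washout. That statement should settle whether clinicians recommend stopping. No date or washout length is proposed here.
2. Whatever rule results, confirm at Baseline that it is still met, using the Concomitant Medications form already completed at that visit, and mark Inclusion/Exclusion Criteria at Baseline in Table I.

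The cost is wording in those sections, one extra mark in Table I and a brief eligibility confirmation; no visit, test or form is added. The downside is a rare late screen failure. A Baseline check does not address a drug begun during the eight treatment weeks, which is a separate question.

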1.1. Study Visits

Study visits will occur entirely via TeleHealth or Zoom, which is maintained by Partners HealthCare. In the event that TeleHealth or Zoom malfunction or a subject loses access to a device compatible with these platforms at scheduled time, the study visit will be rescheduled. The study involves screening, baseline, and a series of clinical monitoring and follow up visits.

Screening Process (Week 99)

The screening process includes the following components:

- Subjects will virtually meet with a study clinician for a psychiatric evaluation and review of medical history.
- The study clinician will ask the participant about his or her symptoms of autism spectrum disorder.
- The study clinician will ask the participant about his or her symptoms of ADHD.
- The study clinician will ask the participant and their parent/guardian questions regarding their child's reproductive potential. If deemed necessary, female participants of childbearing potential will complete a urine pregnancy test. If a participant has a positive pregnancy test, she will not be able to take part in the study. The study doctor will inform the participant and discuss the clinically appropriate course of action. The participant will be offered 3 follow-up visits.
- We will ask the participant's parent/guardian complete three observer-rated questionnaires about their child's ASD symptoms (SRS-2, CBCL, MGH-SECS). These questionnaires will take approximately 30-40 minutes to complete.
- We will ask the participant's parent/guardian to complete a brief demographic interview collecting information regarding socioeconomic status and history of head injury or trauma. This will take about 5-10 minutes to complete.
- Optional: if an additional parent/caregiver is available, we will ask them to complete one to three observer-rated measures on REDCAP.

We anticipate that subjects may enter this trial following completion of/withdrawal from other protocols in our office, and that there may be procedural overlap. So as to not burden subjects/parents/guardians with redundant time commitments, we will use the following diagnostic data previously collected: If a subject has completed an evaluation with one of the study clinicians in the three years preceding their entrance to the study, they will not be asked to repeat these overlapping diagnostic procedures. We will use the study diagnostic data previously collected so as to not burden the subject with redundant time commitments. However, the study clinician will review the interval time period to assess for clinically significant medical or psychiatric history to ensure that the subject meets appropriate study entrance criteria.

Study participants and/or their legal guardians may request the results of their cognitive testing. In this case, the subject will receive a letter providing a basic interpretation of the results and referring them to the department's supervising neuropsychologist for any questions or concerns.

Photobiomodulation for ASD in ADHD

The following assessments will be performed at the Screening Visit:

- CGIs
- GAF
- CTAE
- Concomitant Medications
- Demographic Interview
- SRS-2 (Pre-Screening)
- CBCL
- MGH-SECS-I
- MGH-SECS-C
- BRIEF-P

Study Treatment Phase (Weeks 0-8)

Pregnancy potential will be monitored at screening, baseline, Week 2, Week 4, and Week 6 by a clinician-rated reproductive potential form. If, during any of these visits the participant is deemed to have pregnancy potential, a member of study staff will contact the participant and their parent/guardian to complete a phone screen to ensure the participant and their parent/guardian understand why a urine pregnancy test is necessary, explain the required procedures, and obtain verbal consent from both the parent/guardian and the subject to send the urine pregnancy test to their home address. If both the parent/guardian and the participant provide verbal consent, a pregnancy test will be overnight shipped using study funds and sent directly to the subject's home address within 24 hours. The participant will be asked to stop treatment until the urine pregnancy test is performed. In addition, a phone call will be set up at a specified time the next day. During this call, the study coordinator will review the procedure for completing the urine pregnancy test while on the phone and have the subject complete the test while remaining on the line. The subject/subject's parent or guardian will verbally report the result to the study coordinator, and will also send visual confirmation (i.e. a photo of the test with results send via secure email) prior to continuing the study treatment. If the participant and/or their parent/guardian decide that they no longer feel comfortable completing the urine pregnancy test, they will be withdrawn from the study.

The primary investigator may determine that a subject can verbally and visually report the results of the pregnancy test without their parent/guardian. This determination will be made based on clinical judgment, including the patient's report of previous illness and their reliability in reporting symptoms.

Baseline Visit (Week 0)

The overall baseline session is estimated to last about 60 minutes. The subject will be virtually examined to inspect the sites of application (left and right forehead) for any possible skin lesions (e.g. laceration or signs of inflammation) which would contraindicate the treatment. The subject will then be instructed on the appropriate administration of tPBM.

Photobiomodulation for ASD in ADHD

The treatment device is classified as an “Exempt” device in accordance with the requirements of the international standard EN 62471 – Photobiological safety of lamps and lamp systems and, when used correctly, the output is less than the maximum permissible exposure (MPE) no special controls are needed for the environment it is to be used in. At the time of study implementation, the staff will be provided training on basic safety procedures relative to the use of the device. The staff will then virtually instruct the subject’s parent/guardian on the administration of the tPBM such that the headband is appropriately placed. The delivery of the tPBM is expected to last 10-40 minutes total (simultaneous application on the left and right forehead). The subject will be asked to rest for five minutes after the delivery of tPBM. Sites of application will be inspected at each study visit.

Subjects will be instructed to administer the treatment sessions daily for eight weeks, with each session lasting 10-40 minutes. Subjects will be instructed to contact the investigator or a member of his staff at any time between visits concerning adverse events or worsening of symptoms.

Following assessments will be performed at the Baseline Visit:

- CGI
- GAF
- CTAE
- Concomitant Medications
- ADHD-SC

Study Treatment: Virtual Clinical Monitoring Visits (Weeks 1-6)

There are 5 monitoring visits scheduled at Week 1, Week 2, Week 4 (Midpoint), Week 6, and Week 8.

Participants will be prescribed to administer study treatments at home daily for a period of 8 weeks. Study visits will have a visit window of +/- 3 days to facilitate scheduling.

During the visits, the participants will be asked questions about the symptoms of ADHD and ATs and general health in addition to any present side effects or changes in their medications. At weeks 2, 4 (Midpoint), and 6 the participant will be asked to fill out questionnaires.

Following assessments will be performed at the Week 1, Week 2, Week 3, and Week 6 Visits:

- CGI
- GAF
- CTAE
- Concomitant Medications
- TSRQ

Following assessments will be performed at the Midpoint (Week 4) Visit:

- CGI
- GAF
- CTAE
- Concomitant Medications
- ADHD-SC
- SRS-2

- BRIEF-P
- TSRQ
- CBCL

